8.5.3 Laboratory assessments

Clinical laboratory data will be summarized for Safety analysis set and the Add-on Treatment set (as applicable).

Clinical laboratory data to be summarized includes hematology (for IAs, only Hemoglobin, White Blood Cells (WBC), Absolute Lymphocytes Count, Absolute Neutrophils Count, and Platelets will only be presented). For CSR, all parameters planned as per protocol will be presented), clinical chemistry (for IAs, only Total Bilirubin, Aspartate aminotransferase (AST), Alanine aminotransferase (ALT), Lipase, Lipase pancreatic, Amylase, Creatine kinase and Creatinine will be presented. For CSR, all parameters planned as per protocol will be presented), and urinalysis. The safety laboratory parameters to be assessed are listed in Section 10.2 of the protocol amendment. The scheduled time points for assessment are outlined in the SoAs (Section 10.4).

Safety laboratory parameters at each visit and change from baseline to each post-baseline visit will be summarized using descriptive summary statistics for each parameter by treatment group.

If a laboratory value is reported using a nonnumeric qualifier e.g., less than (<) a certain value, or greater than (>) a certain value, the given numeric value will be used in the summary statistics, ignoring the nonnumeric qualifier.

In case there are several results for the same parameter at the same visit, the record from the central lab will be used for the analyses. The local lab results will be only listed.

Safety laboratory results will be classified according to the most recent version of NCI-CTCAE. Shift tables from baseline to worst grade on treatment will be provided for each laboratory parameter by randomized treatment group.

Laboratory values that are below or above the reference ranges will be flagged.

Abnormal and clinically significant, abnormal and not clinically significant and normal laboratory values will be summarized for each urinalysis parameter by visit and randomized treatment group.

In addition, clinically laboratory values for each parameter will be plotted using trellis plots. Maximum post baseline values will be displayed vs baseline value by treatment group. The

Statistical Analysis Plan (SAP) BNT111-01

Page 50 of 78 Version: Final v7.0 Date: 05Mar2024

plots will be repeated for minimum post baseline values vs baseline value by treatment group.

Notes for programming: For lab summary by visit tables: for baseline visit under value statistic, include all subjects having non-missing baseline data; for post-baseline visit under value statistic, include all subjects having non-missing post-baseline data; for post-baseline visit under CFB statistic, include subjects having both baseline and post-baseline data.

The data as collected will be presented in the listings along with the reference ranges and CTCAE grade. Laboratory values that are below or above the reference ranges will be flagged. Laboratory listings will be presented similarly to the laboratory tables, for IAs the same parameters as present in the tables will be presented. For the CSR all parameters planned as per protocol will be presented.

8.5.4 Vital signs

Vital sign parameters to be summarized by treatment group include systolic blood pressure, diastolic blood pressure, heart rate, respiratory rate and body temperature.

Vital sign parameters at each visit will be summarized using descriptive summary statistics for each parameter as follows:

- change from baseline to each post-baseline visit, considering the value at 60-min prior treatment at Cycle 1, Day 1 as the baseline value (see Section 8.1 for definition of baseline). For post-baseline visits where treatment is administered, the 60-min prior treatment value at each post-baseline to be the visit value. Else the value collected at the visit will be used.
- change from pre-treatment value (60-min prior treatment) at each visit to each posttreatment time point value at that visit. So, considering the 60-min prior treatment value at a visit as the baseline for that visit for this calculation

Additionally, the occurrence of normal, abnormal clinically significant, abnormal not clinically significant results will be analyzed as categorical data for each parameter by visit and treatment group.

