2.3.1 Risk assessment

Expected adverse drug reactions (ADR) for BNT111 are fever, chills, lymphopenia, increase of cytokines and dizziness, not considered to have a significant impact on the risk-benefit profile of the product. NCI-CTCAE Grade 2 or 3 hypotension was seen in 8% of patients within 4 to 6 h after BNT111 administration, typically after the first or second vaccination, and patients with hypotension responded well to fluids. In rare cases, more severe events of cytokine release syndrome associated with pyrexia, hypotension, and hypoxia of higher NCI-CTCAE grades occurred. The onset was sometimes sudden; vital signs should therefore be carefully monitored for 6 h after at least the first three vaccinations.

Immune-related adverse reactions can occur with cemiplimab. Most of these, including severe reactions, resolved following initiation of appropriate medical therapy or withdrawal of cemiplimab. The most common immune-related adverse reactions seen in clinical trials (591 patients) were hypothyroidism (7.1%), pneumonitis (3.7%), immune-related skin adverse reactions (2.0%), hyperthyroidism (1.9%) and hepatitis (1.9%). Adverse reactions were serious in 8.6% patients and led to permanent discontinuation of cemiplimab in 5.8% of patients. See Section 6.8.4.2 for special warnings and precautions.

BNT111 has been given in combination with anti-PD-1 therapy in the Lipo-MERIT trial, no increase of AEs for any of the components was seen for the combination therapy compared to monotherapy. Safety data from the BNT111-01 trial interim analysis was in line with that observed in the Lipo-MERIT trial (Section 5.2 of the BNT111 IB). Based on the available safety data on TESAEs and treatment-emergent deaths, no safety signal was detected which would change the safety profile or benefit/risk assessment of BNT111 established in Lipo-MERIT trial. This was supported by the outcome of all IDMC meetings that recommended to continue the trial without modification.

Page 39 of 133 Version: 7.0 Date: 09 FEB 2023

Table 1: Summary of important, potential risks and mitigation actions taken

Potential risks	Actions taken	
General safety	An IDMC manages all potential safety concerns in this trial.	
Risks related to cancer vaccine antigen targets or anti-PD-1 therapy	Patients with clinically relevant autoimmune diseases are excluded from the trial.	

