	•	Occurrence of dose reduction and discontinuation of trial treatment within a patient due to TEAE.
	•	Changes in laboratory parameters compared to baseline.
	•	Occurrence of abnormal laboratory parameters within a patient.
	•	Changes in vital signs parameters compared to baseline.
	•	Occurrence of abnormal vital signs parameters within a patient.
Assess health-related quality of life (HRQoL) of patients treated with		Mean changes from baseline in the global health status score of the EORTC QLQ-C30*
BNT111 + Cemiplimab (Arm 1) and of patients receiving BNT111 and cemiplimab as single agents as measured by the European organization for research and treatment of cancer quality-of-Life questionnaire core 30 items (EORTC QLQ-C30).	•	Mean changes from baseline in scores of the EORTC QLQ- C30 functional and symptoms scales*
	•	Time to first clinically meaningful deterioration in global health status score as measured by EORTC QLQ-C30
	•	Time to first clinically meaningful deterioration in symptoms and functioning as measured by EORTC QLQ-C30*
Exploratory Objectives	Endpo	ints
Assess the anti-tumor activity of BNT111 + Cemiplimab (Arm 1) as well as each single agent (i.e., BNT111 and cemiplimab) according to iRECIST.	٠	ORR, DOR, DCR, TTR, PFS as assessed by BICR and the investigator.
Assess additional measures of anti- tumor activity of BNT111 + Cemiplimab (Arm 1), and each single agent (i.e., BNT111 and cemiplimab) according to RECIST 1.1/iRECIST.	•	Depth of response as defined by maximum percentage reduction from screening/baseline* in the size of the tumor as assessed by BICR and the investigator.

Statistical Analysis Plan (SAP) BNT111-01

Page 14 of 78 Version: Final v7.0 Date: 05Mar2024

Objectives	Endpoints		
Assess the anti-tumor activity during add-on BNT111 + Cemiplimab (Arm 2 and 3) according to RECIST 1.1/ iRECIST.	 ORR, DOR, DCR, TTR, PFS as assessed by BICR and the investigator. 		
Assess overall survival of each single- agent (i.e., BNT111 and cemiplimab, respectively) with or without add-on treatment (Arm 2 and 3)	• OS		
Assess systemic induction/expansion of BNT111 antigen-specific T cells.	 Patients in biomarker sub-trial (selected trial sites): Occurrence of de novo induction of increase in expansion of BNT111 antigen-specific T cells under treatment compared 		

Characterize the pharmacodynamic profile of BNT111 in combination with Cemiplimab (Arm 1 and add-on treatment) and identify potential predictive biomarkers for efficacy.

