An analysis update will be performed when the last patient discontinued from the trial and once all patients have been randomized and have been followed-up for at least 24 months. An analysis update may be subsequently performed.

Statistical Analysis Plan (SAP) BNT111-01

Page 30 of 78 Version: Final v7.0 Date: 05Mar2024

Data up to and including the clinical cut-off date will be taken into account for the statistical analysis.

All analyses will be conducted using SAS® version 9.4 or higher.

Baseline is defined as last non-missing value prior to the first dose of trial treatment at C1D1. Assessments performed at C1D1 will be considered for baseline value, unless there is evidence the assessment was performed after trial treatment had been administered. For the add-on treatment if the baseline visit and AOC1D1 are on the same day, the assessment only needs to be taken once. In this case the AOC1D1 would be considered as the baseline value, unless there was evidence that the assessment was done after treatment had been administered.

To identify the baseline value, generally, if there are multiple assessments available for a particular day, the assessment that is closest to the day (and time if collected) of the first dose of the trial treatment (i.e., BNT111 or cemiplimab) will be used as the baseline value in the summary/analyses.

Multiple values at post-baseline visits: if there are multiple post-baseline assessments available within a visit/day, the first value and corresponding date/time will be considered.

Change from baseline will be calculated as follows:

Change from baseline = post-baseline assessment value – baseline assessment value.

If either the baseline or post-baseline assessment value is missing, the change from baseline is set to missing as well.

Duration (Other than "trial treatment duration" defined in Section 8.5.1) will be calculated as follows:

Duration = last observation date - first observation date + 1

For conversion of days to months or years the following rules will be applied:

- 1 month = 30.4375 days
- 1 year = 365.25 days

Trial Day and Treatment Day are defined as follows:

- Trial day:
 - If assessment date < randomization date then trial day = assessment date randomization date
 - If assessment date >= randomization date then trial day = assessment date randomization date + 1
- Treatment Day = treatment date date of first dose +1

That is, trial day 1 indicates the date of treatment initiation.

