All trial data will be presented at the visit as collected in the eCRF. No windowing of data for the purposes of assigning to a visit will occur.

Statistical Analysis Plan (SAP) BNT111-01

Page 31 of 78 Version: Final v7.0 Date: 05Mar2024

Unscheduled assessments will be included in the analysis of efficacy endpoints for tumor response, time to event endpoints and shift from baseline to worst NCI-CTCAE Grade laboratory summary tables. All other unscheduled assessments will be listed only and not included in summaries/analysis.

If there is a difference between randomized and actual strata at randomization then the randomized strata will be used for analyses. A summary of randomized and actual strata at randomization will be presented. If there is a notable difference between the two summaries, then a sensitivity analysis for the primary endpoint will be considered.

Handling missing Data:

For the purposes of assigning treatment-emergent flag for AEs, partial or missing AE dates will be handled as follows:

- If the day of the month is missing, the onset day will be set to the first day of the
 month unless it is the same month and year as the first trial treatment. In this case,
 in order to conservatively report the event as treatment-emergent, the onset date will
 be assumed to be the date of the first trial treatment.
- If the onset day and month are both missing, the day and month will be assumed to be January 1, unless the event occurred in the same year as the first trial treatment.
 In this case, the event onset will be assumed to be the day and month of treatment in order to conservatively report the event as treatment-emergent.
- A completely missing onset date will be assumed to be the day of the first trial treatment.
- If an AE has a partial start date that is in the same month/year as the first dose of trial treatment, then the AE will be reported as treatment-emergent. If an AE has a missing start date, then the AE will be reported as treatment-emergent.

For the purposes of assigning treatment-emergent flag for irAEs, partial or missing irAE dates will be handled as follows:

- If the day of the month is missing, the onset day will be set to the first day of the
 month unless it is the same month and year as the first trial treatment of cemiplimab.
 In this case, in order to conservatively report the event as treatment-emergent, the
 onset date will be assumed to be the date of the first trial treatment of cemiplimab.

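### SAP 8.5.4 does not say which reading feeds the vital-sign abnormality table; under the SAP's own default the 4 h and 6 h post-dose readings would drop out, and no per-patient count is planned

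*SAP*

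**What the plan says.** SAP 3.1, like Protocol Section 3, lists as a secondary safety endpoint: "Occurrence of abnormal vital signs parameters within a patient". Protocol 9.4.5 keeps the within-patient idea and plans the summary by parameter, visit and treatment group. It does not limit the summary to pre-dose readings.

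The schedule of activities (footnote n to SOA1 in both documents) asks for one reading in the hour before dosing and four after it, at 30 min, 60 min, 4 h and 6 h. Protocol 6.8.4.1 lets sites skip the 4 h and 6 h readings after an uneventful first cycle and allows an optional 24 h reading.

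SAP 8.5.4 has three parts:

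1. Change from baseline by visit. Inside this bullet stands: "For post-baseline visits where treatment is administered, the 60-min prior treatment value at each post-baseline to be the visit value".
2. Post-dose change: "change from pre-treatment value (60-min prior treatment) at each visit to each posttreatment time point value at that visit".
3. A separate sentence for the abnormality table, which is split by treatment group: "the occurrence of normal, abnormal clinically significant, abnormal not clinically significant results will be analyzed as categorical data for each parameter by visit".

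SAP 8.1 adds two general rules. For repeated values, "if there are multiple post-baseline assessments available within a visit/day, the first value and corresponding date/time will be considered". For unscheduled data, after exceptions for tumor response, time-to-event endpoints and the laboratory worst-grade shift tables: "All other unscheduled assessments will be listed only and not included in summaries/analysis".

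**The concern.** For hypotension of Grade 2 or 3, Protocol 2.3.1 reports that it "was seen in 8% of patients within 4 to 6 h after BNT111 administration, typically after the first or second vaccination". A table that classifies one pre-dose reading per visit describes patients one or three weeks after their previous dose. It does not describe their reaction to the dose just given. If the table is built that way, the endpoint best placed to show acute hypotension and fever would largely miss both.

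The wording is also loose enough that two competent programmers could build different tables from it, one on the pre-dose reading and one on all readings.

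Laboratory data are treated more fully. SAP 8.5.3 plans shifts to the worst grade on treatment and plots of the post-baseline minimum and maximum, and SAP 8.1 lets unscheduled results into the shift tables. Vital signs get no worst-value summary.

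**Working it through.** The documents give no figure for this endpoint, so there is none to reproduce. The check sets the rules side by side and then gives a sense of scale.

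**Step 1: which reading would be classified?** The abnormality sentence names no time point and no worst-value rule. Two SAP rules choose among readings:

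| Visit | 8.5.4 visit-value wording, if carried over | 8.1 first-value default, if applied |
|---|---|---|
| C1D1 | pre-dose reading is the baseline; no post-dose reading chosen | pre-dose reading is the baseline, so the first post-baseline value is the 30-min reading |
| Dosing visits after C1D1 | pre-dose | pre-dose |

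No SAP rule selects a 4 h or 6 h reading for this table. At a dosing visit after C1D1, four of the five scheduled readings (4/5 = 80%) would go unused. At C1D1, at most one of the four post-dose readings would be used.

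Whether the optional 24 h reading counts as unscheduled is not stated. If it does, it is listed only.

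**Step 2: how many patients could this concern?** Inputs:

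- 90 patients in Arm 1 and 45 in Arm 2 (SAP Table 3.2), so 135 randomized to BNT111.
- A rate of 8% for Grade 2 or 3 hypotension (Protocol 2.3.1; Section 2.1.2 attributes it to the Phase I trial).
- Assumption: the rate carries over. The range of 4% to 12% is also assumed.

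Expected number affected = n × p:

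| n | 4% | 8% | 12% |
|---|---|---|---|
| 90 (Arm 1) | 3.6 | 7.2 | 10.8 |
| 135 (Arms 1 and 2) | 5.4 | 10.8 | 16.2 |

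Chance of at least one case in Arm 1 = 1 − (1 − p)^90, which is 0.9994 at 8% and 0.9746 at 4%.

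These are patients expected to have the event, not a count of patients missed. A pre-dose table would show such a patient only if a pre-dose reading was also abnormal. At C1D1 a fall already present at 30 min could be picked up under the 8.1 default.

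**Step 3: does the table answer the endpoint?** The endpoint is per patient. A by-visit table counts a patient abnormal at two visits once in each, and different patients may be abnormal at different visits. The number with at least one abnormal reading therefore lies somewhere between the largest by-visit count and the sum of those counts, and the table cannot fix it. This gap does not depend on Step 1.

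**The case against.** A reader might infer that the SAP prescribes the pre-dose reading for this table, so that post-dose hypotension and fever can never enter the endpoint. The text does not support that:

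- The visit-value wording sits in the change-from-baseline bullet. The abnormality sentence is separate, speaks of results, and could be programmed on all time points.
- The 8.1 first-value rule cannot bind everywhere in 8.5.4, because the second bullet needs several values per visit. Even where it applies, it could admit the 30-min reading at C1D1.
- Post-dose data are not reduced to a mean. SAP 8.1 defines summary statistics to include the minimum and maximum, so the second bullet shows the largest fall or rise at each post-dose time point by arm. It would be wrong to conclude that the BNT111 arms must look like Arm 3 across the vital-sign output.
- Clinically significant abnormalities are recorded as adverse events (Protocol 8.2.3), as are otherwise unexplained abnormalities that lead to medical intervention (Protocol 10.3.1.9). Protocol Table 6 describes Grade 2 and 3 hypotension as calling for intervention, so such cases should appear in the per-patient tables of SAP 8.5.2.
- The by-visit layout follows Protocol 9.4.5.

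All of this stands, and it limits the point without removing it. The second bullet overrides the default explicitly; the abnormality sentence does not, so the default is the natural reading. A minimum or maximum shows an extreme but not how many patients had one. Adverse-event tables leave out findings judged not clinically significant (Protocol 10.3.1.7), and an abnormality that is a sign of a syndrome is recorded only under the diagnosis (Protocol 10.3.1.9). Protocol 9.4.5 asks for within-patient occurrence as well as a by-visit layout.

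**Conclusion.** The point holds as a gap in specification with a likely adverse default. SAP 8.5.4 leaves open which reading is classified, and the rules available to fill the gap lead to the pre-dose reading after C1D1 and at most the 30-min reading at C1D1. The 4 h and 6 h readings would then not count. That the table will be built this way is an inference; the SAP does not state it.

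Independently of that inference, the plan contains no count of patients with at least one abnormal vital sign, which is what the endpoint names.

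The scale is about 7 of 90 Arm 1 patients with post-dose Grade 2 or 3 hypotension, or 3.6 to 10.8 over the assumed range. This rests on carrying over a Phase I rate and covers hypotension only; no rate was used for fever. The events would still be visible in part through the post-dose change summaries, the adverse-event tables and the listings. What is at stake is whether this secondary endpoint reports what it says it reports, not whether acute reactions are detected at all.

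**What to change.** In SAP 8.5.4:

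- State that the 8.1 first-value rule does not apply to the abnormality table.
- Classify each dosing visit by the worst post-dose reading. Include the C1D1 post-dose readings and any 24 h or unscheduled readings, with a matching exception to the listed-only rule in 8.1.
- Show the pre-dose classification separately.
- Add, per parameter and arm, the number of patients with at least one abnormal reading and with at least one clinically significant abnormal reading after first dose.

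The cost is SAP wording and one reprogrammed table, with no new data collection.

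The drawback is unequal opportunity. Arm 3 has no Day 8 and Day 15 visits, so counting one set of readings per visit, the first cycle gives 3 × 4 = 12 scheduled post-dose readings in Arms 1 and 2 against 1 × 4 = 4 in Arm 3. More readings mean more chances of an abnormal value, so the number of readings per arm should be shown beside the counts.

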8.5.5 ECG

ECG parameters to be summarized include QT, QTcF, PR, and QRS intervals in msec, heart rate (bpm).

ECG parameters will be summarized by presenting summary statistics of the observed and change from baseline values by visit and treatment group.

Investigator interpretation of ECGs will be summarized as for categorical data by treatment group for each visit.

8.5.6 ECOG performance status

The ECOG performance status is a rating scale used to assess how a patient's disease is progressing as well as how the disease affects the daily living abilities of the patient. The

Statistical Analysis Plan (SAP) BNT111-01

Page 51 of 78 Version: Final v7.0 Date: 05Mar2024

score values are 0 - 5, where 0 indicates "fully active, able to carry on all pre-disease performance without restriction" and 5 indicates the patient has died.

ECOG will be summarised as categorical data by treatment group and visit. Additionally, a shift table from baseline to each visit by treatment will be provided.

A listing of ECOG performance status will also be provided.

